7.2 Serious adverse events

7.2.1 Definitions

A SAE is defined as an event that meets at least 1 of the following criteria

- Is fatal or life-threatening
- Requires inpatient hospitalization or prolongation of existing hospitalization, unless hospitalization is a result of:
 1. A routine treatment or monitoring of the studied indication not associated with any deterioration in condition
 2. An elective or preplanned treatment for a pre-existing condition that is unrelated to the indication under study and has not worsened since signing the ICF
 3. A treatment on an emergency outpatient basis for an event not fulfilling any of the definitions of a SAE and not resulting in hospital admission
 4. Any social reasons and respite care, in the absence of any deterioration in the subject's general condition
- Results in persistent or significant disability, incapacity, or a substantial disruption of a person's ability to conduct normal life functions
- Constitutes a congenital anomaly or birth defect
- Is considered to be an important medical event or a medically significant event that may not result in death, be immediately life-threatening, or require hospitalization but may be considered serious when, based upon appropriate medical judgment, the event may jeopardize the subject or may require medical or surgical intervention to prevent 1 of the outcomes listed above.

7.2.2 Reporting

- Information about all SAEs is collected and recorded on the Adverse Event Form of the CRF. The investigator must assess and record the causal relationship of each SAE to the treatment. SEA must be reported in compliance with institutional IRB/DSMD requirements.

- Investigational site personnel must report any new information regarding the SAE within 24 hours of becoming aware of the information in the same manner that the initial SAE Report Form was sent. Follow-up information is recorded on an amended or new SAE Report Form, with an indication that it is follow-up to the previously reported SAE and the date of the original report. The follow-up report should include information that was not provided on the previous SAE Report Form, such as the outcome of the event (eg, resolved or ongoing), treatment provided, action taken with study drug because of the SAE (eg, dose reduced, interrupted, or discontinued), or subject disposition (eg, continued or withdrew from study participation). Each recurrence, complication, or progression of the original event should be reported as follow-up to that event, regardless of when it occurs.

7.3 Data Safety Monitoring Board (DSMB)

This study will be approved and monitored by the HackensackUMC DSMB. The DSMB is responsible for the monitoring of investigator initiated research studies to ensure the safety of participants, the integrity of the data, and the appropriate termination of studies in the event that undue risks have been uncovered, or it appears that trials cannot be conducted successfully. The DSMB provides multidisciplinary, independent oversight of research studies conducted by HackensackUMC staff and or affiliates. The DSMB can require protocol modifications related to participant safety and to recommend suspension or termination to the IRB and institutional official of any research protocols that fall within its jurisdiction. The DSMB may request that HackensackUMC's Corporate Compliance Department conduct periodic audits to assure that data are being collected and recorded according to the protocol.

The investigator is required to submit monthly monitoring reports which include current enrollment data, adverse event summary data and any other data requested by the DSMB. The DSMB will meet monthly to review the trial progress, adverse event data, and any relevant information such as significant amendments or reviews from IRB submitted by the principal investigator. If significant concerns are raised by the DSMB, the concerns will be forwarded to the PI as well as recommendations made to the IRB, and Institutional Official. Recommendations may include modifying, suspending, or terminating the protocol.

8. Study Design and Sample Size Considerations

This is a randomized phase II trial to assess the efficacy and safety of treatment with convalescent plasma infusion (Treatment) versus without convalescent plasma infusion (Control) in patients with early COVID-19 infection at high-risk of admission. Eligible subjects will be stratified randomized by their Charlson Comorbidity Index scoring in a 1:1 ratio to receive either Treatment or Control (8.4). For this trial, we have considered a group sequential design which has more interim analyses and utilized a three-stage O'Brien-Fleming design.²³

8.1 Hypothesis

The primary objective is the hospitalization rate of patients with early COVID-19 infection at high-risk of admission. Suppose the hospitalization rate by 21 days from therapy initiation is 8% for the Treatment group (P_t) and 18% for the Control group (P_c). This phase II design will aim at the following hypothesis:

The design has a type I error rate at 0.05 with statistical power at least 0.80.

8.2 Study design

This trial will follow a one-sided three-stage O'Brien-Fleming design as follows.²³

The first stage analysis will be after 51 subjects in each arm, that is after a total of 102 subjects. If the Z statistic is greater than or equal to 0.179 (p-value ≥ 0.571), the hypothesis H_0 is accepted and the trial stops, we conclude the Treatment is not worth pursuing; if the Z statistic is less than or equal to -2.849 (p-value ≤ 0.002), the hypothesis H_0 is rejected and early evidence for promising efficacy is established. Otherwise, the trial continues to the next stage.

The second stage analysis will be after 102 subjects in each arm, that is after a total of 204 subjects. If the Z statistic is greater than or equal to -0.944 (p-value ≥ 0.173), the hypothesis H_0 is accepted and the trial stops, we conclude the Treatment is not worth pursuing; and if the Z statistic is less than or equal to -2.015 (p-value ≤ 0.022), the hypothesis H_0 is rejected and early evidence for promising efficacy is established. Otherwise, the trial continues to the final stage.

At the final stage, a total of 306 subjects will be recruit and 153 of them for each arm. The hypothesis H_0 is rejected for efficacy if the Z statistic is less than -1.64504 (p-value < 0.4498). Otherwise, the H_0 is not rejected.

Stage	Cumulative total sample size N	Cumulative sample size for treatment group N(Grp 1)	Cumulative sample size for control group N(Grp 2)	Evidence for undesired rate if Z statistic \geq (Accept H_0 if Z-statistic \geq)	Evidence for desired rate if Z statistic \leq (Reject H_0 if Z-statistic \leq)	Evidence for undesired rate if p-value \geq (Accept H_0 if p-value \geq)	Evidence for desired rate if p-value \leq (Reject H_0 if p-value \leq)
1	102	51	51	0.17929	-2.84929	0.57115	0.00219
2	204	102	102	-0.94399	-2.01475	0.17259	0.02197
3	306	153	153	-1.64504	-1.64504	0.04998	0.04998

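### The final-stage efficacy rule prints a p-value threshold of 0.4498 beside a Z bound whose p-value is 0.04998; applied literally, it would raise the type I error from 0.05 to about 0.16

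*Combined protocol and SAP*

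**What the plan says.** Section 8.1 sets the operating characteristics: "The design has a type I error rate at 0.05 with statistical power at least 0.80". It assumes that the hospitalization rate "is 8% for the Treatment group (P_t) and 18% for the Control group (P_c"). Section 8.2 names the design: "This trial will follow a one-sided three-stage O'Brien-Fleming design as follows".

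The final-stage rule, at 153 subjects per arm, is that the null hypothesis is "rejected for efficacy if the Z statistic is less than -1.64504 (p-value < 0.4498"). The Statistical Analysis part of the Protocol Summary gives the same rule with the same two numbers.

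The table in section 8.2 differs. Its stage 3 row gives -1.64504 as both the accept and the reject bound on the Z scale, and 0.04998 as both bounds on the p-value scale. The Protocol Summary has no such table.

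**The concern.** One sentence gives two rejection criteria for the primary hypothesis, and they are not the same criterion. A result of Z = -0.5 (one-sided p = 0.31) fails by the Z bound and succeeds by the printed p-value. The plan does not say which scale governs.

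This is the trial's last decision threshold. Section 8.3.1 specifies a Mantel-Haenszel test for the primary endpoint. Such a test is usually read from its p-value, so the wrong half of the sentence could be the half that is applied. In that case the 0.05 error rate in section 8.1 would not hold. Even if nobody applied it, a prespecified rule should not have to be interpreted after the data are seen.

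**Working it through.** **Inputs, all from section 8.2 unless noted**

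- One-sided test, 1:1 allocation, efficacy in the lower tail.
- Cumulative subjects per arm of 51, 102 and 153, so the information fractions are 51/153 = 1/3, 102/153 = 2/3 and 1.
- Efficacy bounds a1 = -2.84929 and a2 = -2.01475; final bound c = -1.64504.
- Futility bounds b1 = 0.17929 and b2 = -0.94399. They are treated as binding because the text says the trial stops when they are crossed.
- Target type I error 0.05 (section 8.1).

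**Step 1: convert each Z bound to a p-value, p = Φ(Z)**

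| Bound | Z | Φ(Z) | Table | Narrative text |
|---|---|---|---|---|
| Stage 1 futility | 0.17929 | 0.57115 | 0.57115 | 0.571 |
| Stage 1 efficacy | -2.84929 | 0.00219 | 0.00219 | 0.002 |
| Stage 2 futility | -0.94399 | 0.17259 | 0.17259 | 0.173 |
| Stage 2 efficacy | -2.01475 | 0.02197 | 0.02197 | 0.022 |
| Final | -1.64504 | 0.04998 | 0.04998 | **0.4498** |

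Only the final narrative value fails, by a factor of 0.4498/0.04998 = 9.0. In the other direction, Φ⁻¹(0.4498) = -0.126. A dropped zero does not explain it: Φ⁻¹(0.04498) = -1.696, which also misses the Z bound.

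**Step 2: confirm that -1.64504 is the intended bound**

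O'Brien-Fleming efficacy bounds satisfy |a_k|·√t_k = constant, where t_k is the information fraction at stage k.

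- Stage 1: 2.84929 × √(1/3) = 1.64504.
- Stage 2: 2.01475 × √(2/3) = 1.64504.
- Stage 3: 1.64504 × 1 = 1.64504.

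The Z bound fits the design.

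**Step 3: reproduce the plan's own type I error**

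Under the null, (Z1, Z2, Z3) is multivariate normal with mean zero and correlation √(t_j/t_k) for j < k. Then

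α = P(Z1 ≤ a1) + P(a1 < Z1 < b1, Z2 ≤ a2) + P(a1 < Z1 < b1, a2 < Z2 < b2, Z3 ≤ c).

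Recursive numerical integration with c = -1.64504 gives

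0.00219 + 0.02051 + 0.02730 = 0.0500.

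The stated 0.05 is reproduced. Power at 8% versus 18% is 0.794 with a pooled variance and 0.802 with an unpooled variance, in line with the stated 0.80.

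**Step 4: the same calculation with the printed p-value, c = -0.126**

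0.00219 + 0.02051 + 0.13259 = 0.1553.

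The probability of reaching stage 3 and not rejecting is 0.0080. The probability of reaching stage 3 is therefore 0.1326 + 0.0080 = 0.1406, and the share of those null trials declared positive is 0.1326/0.1406 = 94%.

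**Step 5: checks**

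- A simulation of 4 million null trials on the normal scale gave 0.0498 with the Z bound and 0.1551 with the printed p-value.
- Simulated null trials with assumed event rates of 18% and 13% in both arms gave 0.156 and 0.158 with the printed p-value, against 0.050 with the Z bound.
- If the futility stops were ignored as well, the printed p-value would give an overall type I error of 0.450.

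**The case against.** The strongest reply is that nobody would apply the printed figure. The sentence makes the Z statistic the criterion and puts the p-value in brackets. If the Z bound governs, or if both conditions must be met, the rule is still Z < -1.64504 and the type I error stays at 0.050. The surrounding text points the same way: the table directly below gives 0.04998, section 8.1 gives 0.05, and section 8.3.4 uses 0.05 as its general significance level. A final efficacy threshold near 0.45 would also be far looser than the stage 2 futility threshold of 0.173. The inflation also needs context: only about 14% of null trials reach stage 3.

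Most of this stands. The intended value is clear, the design is sound, and the rise to about 0.16 is conditional on the p-value being used in place of the Z bound.

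It does not remove the need for a correction. The wrong figure appears in both narrative statements of the rule, and the Protocol Summary has no table against which to check it. The general 0.05 statement in section 8.3.4 is not said to override the stage-specific rule. The detailed plan promised in section 8.3.1 is for the interim analyses, and nothing says it will restate the final bound.

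**Conclusion.** The concern holds. The final-stage p-value of 0.4498 is wrong wherever it appears; the value that matches the Z bound, the table and the stated error rate is 0.04998. If the Z bound or the table governs, the one-sided type I error is 0.050 as planned. If the printed p-value is applied instead, it is 0.155 by the normal approximation, or 0.156 to 0.158 with simulated event data, about three times the stated level.

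The larger figures assume analyses at 51, 102 and 153 subjects per arm, with the stage 1 and 2 efficacy and futility bounds followed as written. The error is probably typographical, but it sits in the primary decision rule and must be corrected.

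**What to change.** In section 8.2 and in the Statistical Analysis part of the Protocol Summary, replace the final-stage p-value of 0.4498 with a one-sided p-value ≤ 0.04998. State that it is one-sided, because the table's p-values are lower-tail probabilities of Z. For consistency with the table, write the Z condition as ≤ -1.64504 rather than <; this has almost no numerical effect.

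The cost is one figure changed in two places. The sample size, boundaries, analysis times and trial conduct are unaffected, and no new design choice is needed because the correct value is already in the table.

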8.3. Analysis Plan

8.3.1 Primary Endpoints

The primary endpoint of the phase II study is the hospitalization rate at 10 days from therapy initiation of patients with early COVID-19 infection at high-risk of admission. The hospitalization rate will be summarized by frequency (%) and compared between the Treatment and Control arms by Mantel-Haenszel test. There will be two interim analyses. Analysis reports will be provided to the DSMB to decide if there is a pronounced treatment effect or futility. A detailed interim analysis plan will be provided before the start of the interim analysis.

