2.1 Primary objectives

To compare the hospital admission rate of patients with early COVID-19 infection at high-risk of admission with or without convalescent plasma infusion.

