8.3.2 Safety Assessment

Safety assessment will be performed on infusion days 0 (post infusion), +3 and +7 days by telephone (closest business day is acceptable), +2 weeks (+/- 3 days), +4 weeks (+/- 3 days), 2 months (+/- 5 days). The safety of the trial will be accessed by evaluating the therapies exposure, adverse events (AE), and

death. Adverse events that begin or worsen after initiation of plasma donation or infusion should be recorded on the Adverse Events Form of the CRF.

A summarization of the number of days and/or cycles subjects were exposed to the therapies will be provided. AE (and serious adverse events, SAE) will be graded and recorded throughout the study and during the follow-up period according to the NCI Common Terminology for Adverse Events (CTCAE) v4.03. Toxicities will be characterized in terms regarding seriousness, causality, toxicity grading, and action taken with regard to trial treatment. The percentage of subjects experiencing an adverse event at a given severity, an NCI CTCAE toxicity grade, and the relationship to study therapy, will all be provided. And the number of subject deaths throughout the study will be summarized.

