9.2 Institutional Review Board (IRB) Review

- The final study protocol and consent form (and any other appropriate documents as applicable) will be approved by the Institutional Review Board (IRB) at Hackensack Meridian Health. Approval will be received in writing before initiation of the study.
- Any changes to the study design will be formally documented in protocol amendments and will be approved by the IRB prior to implementation.
- Any amendment to this protocol must also be approved by the IRB and FDA. The written signed approval from the IRB should specifically reference the investigator name, protocol number, study title and amendment number(s) that is applicable. Amendments that are administrative in nature do not require IRB approval but will be submitted to the IRB for information purposes.
- The investigator must keep a record of all communication with the IRB and, if applicable, between a Coordinating investigator and the IRB. This statement also applies to any communication between the investigator (or Coordinating investigator, if applicable) and regulatory authorities.
- Any advertisements used to recruit subjects for the study must be reviewed by [sponsor] and the IRB prior to use.

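### The sample size is justified on 21-day hospitalization rates (8.1), but the primary endpoint is set at 10 days (8.3.1), so power for the tested endpoint is unstated

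*Combined protocol and SAP*

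**What the plan says.** Section 8.1 gives the design assumption, "Suppose the hospitalization rate by 21 days from therapy initiation is 8% for the Treatment group", with 18% for Control. It then states: "The design has a type I error rate at 0.05 with statistical power at least 0.80". Section 8.2 turns this into a one-sided three-stage design with looks at 51, 102 and 153 patients per arm: "At the final stage, a total of 306 subjects will be recruit and 153 of them for each arm".

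Section 8.3.1, the analysis plan for the same endpoint, defines it as "the hospitalization rate at 10 days from therapy initiation of patients". It promises more detail on the interim looks: "A detailed interim analysis plan will be provided before the start of the interim analysis".

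The primary objective in 2.1 names no time point: "To compare the hospital admission rate of patients with early COVID-19 infection at high-risk of admission with or without convalescent plasma infusion". The Protocol Summary objective names none either. No visible text connects 10 days with 21 days, gives expected 10-day rates, or states power for a 10-day endpoint.

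**The concern.** The window decides which admissions count. A patient admitted on day 15 is an event under 8.1 and a non-event under 8.3.1. One set of Z boundaries governs the efficacy and futility stops at 102 and 204 patients and the final test at 306, so the choice of window can change whether the trial stops and what it concludes.

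Two things are at stake:

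- **Power.** The 306 patients are justified only for 8% vs 18%, which the text attaches to day 21. The plan does not say what they deliver at day 10.
- **Prespecification.** Under section 4.1 the final analysis waits for the last 2-month visit. Results for both windows will exist by then, and the text would support calling either one primary.

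**Working it through.** **Inputs.** Rates 8% and 18% (8.1). One-sided type I error 0.05 and power of at least 0.80 (8.1, 8.2). Per-arm sizes 51, 102 and 153 (8.2). Reject H0 at Z ≤ -2.84929, -2.01475, -1.64504; accept H0 at Z ≥ 0.17929, -0.94399 at the two interims (8.2 table).

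**Step 1: reproduce the plan's figure.** Drift at the final look = (p_t − p_c) / √{[p_t(1−p_t) + p_c(1−p_c)] / n}. With 8% vs 18% and n = 153:

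(0.08 − 0.18) / √[(0.0736 + 0.1476)/153] = −0.10 / 0.03802 = −2.630.

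Numerical integration over the boundaries at information 1/3, 2/3 and 1 gives rejection probabilities 0.0916 + 0.4625 + 0.2478 = 0.802. With the pooled variance the drift is −2.601 and power is 0.794. Binomial simulation with the pooled Z (1,000,000 trials) gives 0.806, with a futility stop at an interim in 0.046 + 0.083 = 0.129. Under no effect, with futility binding, the type I error is 0.0500. The design therefore reproduces at 8% vs 18%.

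**Step 2: move to day 10.** The documents give no 10-day rates. As an assumption, suppose a share of each arm's 21-day admissions has occurred by day 10, and multiply 8% and 18% by that share. Same design, simulated:

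| Share by day 10, Treatment / Control | 10-day rates | Power | Futility stop at an interim |
|---|---|---|---|
| 100% / 100% | 8.0% vs 18.0% | 0.806 | 13% |
| 90% / 90% | 7.2% vs 16.2% | 0.76 | 16% |
| 80% / 80% | 6.4% vs 14.4% | 0.71 | 19% |
| 70% / 70% | 5.6% vs 12.6% | 0.66 | 23% |
| 50% / 50% | 4.0% vs 9.0% | 0.53 | 32% |
| 80% / 90% | 6.4% vs 16.2% | 0.84 | not tabulated |
| 70% / 90% | 5.6% vs 16.2% | 0.89 | 7% |
| 90% / 80% | 7.2% vs 14.4% | 0.62 | not tabulated |

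Integration with unpooled variance agrees for the equal shares: 0.759, 0.710, 0.654 and 0.521 at 90%, 80%, 70% and 50%.

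**Step 3: break-even.** For power 0.80 with 306 patients, a Control 10-day rate of 16.2% needs a Treatment rate of about 6.8% or less; 14.4% needs about 5.6%; 12.6% needs about 4.4%.

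**The case against.** The strongest reply is that this is a slip of one number. If 8% and 18% were meant for day 10, power is about 0.80 and only 8.1 is wrong. That is possible and the documents cannot exclude it, so the 10-day power is undetermined rather than shown to be lost. One section still has to change, and only the sponsor knows which.

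The shares above are also assumptions, and the protocol's own timing evidence argues against the lowest. Section 1.4 reports that most admitted patients were in their second week of illness. Sections 5.2 and 5.2.2 place infusion within 96 hours of symptom onset, so day 10 after infusion is about day 10 to 14 of symptoms. The 50% row therefore looks extreme, though late second-week admissions could still be missed in patients infused early.

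Three narrower points are fair:

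- Sizing a trial to just meet its power target is normal. The small margin only means there is little to absorb a lower event rate.
- Type I error stays at about 0.05 for either window, provided one is fixed in advance.
- The calculations use an unstratified Z, whereas 8.3.1 names a Mantel-Haenszel test.

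The promised interim analysis plan does not settle the matter. Nothing says it will define the endpoint, and it cannot leave 8.1 and 8.3.1 in conflict.

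**Conclusion.** The inconsistency is real and should be resolved before any interim comparison. The sample size is correct for 8% vs 18%, at whichever window those rates belong to. As written they belong to day 21, while the test is at day 10. Over the scenarios tried, 10-day power runs from 0.53 to 0.89. It falls whenever both arms lose the same share of events, and it can rise if Control admissions come earlier than Treatment admissions. These figures rest on assumed shares, the stated boundaries and an unstratified pooled Z. The contradiction itself rests on no assumption.

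**What to change.** The sponsor should state which window was intended and write it identically in 8.1, 8.3.1 and the interim analysis plan, before the first interim.

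- **If 21 days:** change 8.3.1. The rates, sample size and power stand, and day 10 can be reported as secondary. Visits in 8.3.2 ("4 weeks (+/- 3 days), 2 months (+/- 5 days") already cover it: the 4-week visit falls no earlier than 28 − 3 = day 25, whereas the 2-week visit is too early.
- **If 10 days:** put the expected 10-day rates in 8.1 and restate the power they give with 306 patients, whichever way it moves. If it is below 0.80, the sample size needs review.

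The same edit should define the start of the clock for Control. Both sections count from the start of therapy, which Control patients do not have; section 5.2 makes randomization day 0 for both arms.

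**Cost.** A short text change, but section 9.2 applies: "Any amendment to this protocol must also be approved by the IRB and FDA". It exempts administrative amendments from IRB approval, but a change to the primary endpoint window would hardly qualify. No visits are added. Choosing 21 days delays each interim by at least 21 − 10 = 11 days. Assuming uniform accrual over 10 months (the 12-month duration less 2 months of follow-up), 306 / (10 × 30.4) = 1.0 patient per day, so about 11 more patients are enrolled before each decision. If data are taken only at visits, the nominal delay is 28 − 14 = 14 days, or about 14 patients.
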